Patients will then be contacted by telephone for a follow up visit (visit 6) approximately 12 weeks following the last study visit (visit 5) and will be asked if they had any headaches since the last study visit. For those who experienced headache(s), an additional 12 questions will be asked regarding the number, severity, frequency, and duration of the headache(s) and their effect on daily activities and sleep. Patients will be instructed to return the provisioned devices to the investigational center after collection of the Special Protocol Headache Questionnaire (visit 8).	Patients will be instructed to return the provisioned devices to the investigational center after collection of the Special Protocol Headache Questionnaire (visit 8).	This text was modified to clarify the instructions on returning devices to the investigational center. End of study was changed from visit 6 to visit 8 to reflect the addition of the open-label period. All text relating to the follow-up telephone visit has been removed from the protocol. There will no longer be a telephone follow-up visit.
Section 9.2.4 Per-Protocol Analysis Set		
The per-protocol (PP) analysis set is a subset of the ITT analysis set including only patients without any major protocol deviations or who have unexpected drug concentration findings.	The per-protocol (PP) analysis set is a subset of the ITT analysis set including only patients without any major protocol deviations or unexpected drug concentration findings.	This change was made to clarify which patients are included in the per-protocol analysis set.
Section 9.5.5.1 Primary Efficacy Analysis		
The primary estimand for this study is defined by the following attributes:	The primary estimand for this study is defined by the following attributes:	This change was made as part of a recommendation to include the estimand framework.

Original text with changes shown	New wording	Reason/Justification for change
The target population includes male and female	The target population includes male	
patients aged 18 to 70 years, inclusive, with a	and female patients aged 18 to	
history of PTH (as defined by the ICHD-3 [beta	70 years, inclusive, with a history	
version] criteria).	of PTH (as defined by the ICHD-3	
The primary outcome measure is the mean	[beta version] criteria).	
change from baseline (baseline period) in the	The primary outcome measure is	
monthly average number of headache days of at	the mean change from baseline	
least moderate severity during the 12-week	(baseline period) in the monthly	
period after the first dose of IMP.	average number of headache days	
• The FAS will be used for efficacy analyses. FAS	of at least moderate severity during	
is a subset of the ITT analysis set and includes	the 12-week period after the first	
only patients who receive at least 1 dose of IMP	dose of IMP.	
and have at least 1 postbaseline efficacy	
 
The FAS will be used for efficacy
 
	
assessment on the primary endpoint. In the FAS,	analyses. FAS is a subset of the	
treatment will be assigned based on the treatment	ITT analysis set and includes only	
to which patients were randomized, regardless of	patients who receive at least 1 dose	
which treatment they actually received.	of IMP and have at least	

 
Treatment effect will be measured via ANCOVA
 
	1 postbaseline efficacy assessment	
method, including treatment as fixed effect and	on the primary endpoint. In the	
the baseline number of headache days of at least	FAS, treatment will be assigned	
moderate severity and the PTH onset	based on the treatment to which	
(<12 months and ≥12 months) as covariates.	patients were randomized,	
For patients assigned to active treatment who discontinue the	regardless of which treatment they	
study due to lack of efficacy, death, or adverse event, the	actually received.	
proportion of headache days in the remainder of the analysis	Treatment effect will be measured	
window will be imputed as the mean monthly average of	via ANCOVA method, including	
headache days in the same analysis window for patients	treatment as fixed effect and the	
assigned to placebo. All other missing data for patients in	baseline number of headache days	
either treatment group will be handled as follows:	of at least moderate severity and	
• For patients who have ≥10 days of e-diary data in	the PTH onset (<12 months and	
an analysis window, the monthly average number	≥12 months) as covariates.	
	For patients assigned to active treatment who	

Original text with changes shown	New wording	Reason/Justification for change
of headache days will be calculated based on data	discontinue the study due to lack of efficacy,	
available in that analysis window and prorated to	death, or adverse event, the proportion of	
28 days.	headache days in the remainder of the analysis	
• For patients who have <10 days of e-diary data in	window will be imputed as the mean monthly	
an analysis window, the monthly average number	average of headache days in the same analysis	
of headache days will be imputed as the mean	window for patients assigned to placebo. All	
monthly average of headache days in the same	other missing data for patients in either treatment	
analysis window for patients assigned to the same	group will be handled as follows:	
treatment group and having ≥10 days of e-diary	• For patients who have ≥10 days of	
data. Sensitivity analyses will be conducted as	e-diary data in an analysis window,	
defined in the statistical analysis plan.	the monthly average number of	
	headache days will be calculated	
	based on data available in that	
	analysis window and prorated to	
	28 days.	
	
 
For patients who have <10 days of
 
	
	e-diary data in an analysis window,	
	the monthly average number of	
	headache days will be imputed as	
	the mean monthly average of	
	headache days in the same analysis	
	window for patients assigned to the	
	same treatment group and having	
	≥10 days of e-diary data.	
	Sensitivity analyses will be	
	conducted as defined in the	
	statistical analysis plan.	

Original text with changes shown	New wording	Reason/Justification for change			
Section 9.5.5.2 Sensitivity Analysis					
Sensitivity analysis may be performed will be conducted to	Sensitivity analysis will be conducted to explore	This change was made as part of a recommendation to include the estimand framework.			
explore the impact of missing data in the primary efficacy	the impact of missing data in the primary				
analysis. In particular, endpoints analyzed using an ANCOVA	efficacy analysis. In particular, endpoints				
method will be analyzed using a mixed model for repeated	analyzed using an ANCOVA method will be				
measures method. The details will be described in the	analyzed using a mixed model for repeated				
statistical analysis plan.	measures method. The details will be described				
	in the statistical analysis plan.				
Section 9.5.5.3 Secondary Efficacy Analysis					
For the proportion of responders defined as 50% or more	For the proportion of responders defined as 50%	This change was made as part of a			
reduction from baseline in the monthly average headache days,	or more reduction from baseline in the monthly	recommendation to include the estimand framework.			
the Cochran-Mantel-Haenszel test will be used stratified by	average headache days, the Cochran-Mantel-	frame work.			
PTH onset ( $<12 \text{ months and } \ge 12 \text{ months}$ ).	Haenszel test will be used stratified by PTH				
	onset ( $<12$ months and $\ge12$ months).				
Section 9.6 Multiple Comparisons and Multiplicity					
Testing of statistical significance at a 2-sided alpha of 0.05 will	Testing of statistical significance at a 2-sided	This change was made as part of a			
be performed for the primary endpoint. If the primary endpoint	alpha of 0.05 will be performed for the primary	recommendation to include the estimand framework.			
meets statistical significance, then each of the key secondary	endpoint. If the primary endpoint meets	Hamework.			
endpoints will be tested for significance in a pre-specified	statistical significance, then each of the key				
order at a 2-sided alpha of 0.05. If and when any p>0.05, no	secondary endpoints will be tested for				
further comparisons will be interpreted inferentially. Details	significance in a pre-specified order at a 2-sided				
will be presented in the statistical analysis plan.	alpha of 0.05. If and when any p>0.05, no further				
	comparisons will be interpreted inferentially.				
	Details will be presented in the statistical				
	analysis plan.				
Section 9.9 Pharmacokinetic Analysis					
Pharmacokinetic plasma concentration results for	Pharmacokinetic plasma concentration results for	This text was added to clarify that			
fremanezumab will be tabulated descriptively at each planned sampling time point. At the open-label period, pharmacokinetic	fremanezumab will be tabulated descriptively at each planned sampling time point. At the open-	pharmacokinetic plasma concentration results will be tabulated descriptively at			
plasma concentration results will be tabulated descriptively at	label period, pharmacokinetic plasma	sampling time points.			
each planned sampling time point treatment group.	concentration results will be tabulated				
	descriptively at each planned sampling time				
	point treatment group.				

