A sample size of 154 patients (77 evaluable patients per treatment group) willwas calculated to provide 80% power to detect a treatment difference of 2.0 days in the monthly average (assuming a common SD of 4.4 days) at a 2-sided alpha level of 0.05. Assuming a 10% discontinuation rate, 172 patients (86 patients per treatment group) willwere planned to be randomized in the study.  Study recruitment was discontinued at 87 patients due to challenges to enrollment and not for any safety concerns.	A sample size of 154 patients (77 evaluable patients per treatment group) was calculated to provide 80% power to detect a treatment difference of 2.0 days in the monthly average (assuming a common SD of 4.4 days) at a 2-sided alpha level of 0.05. Assuming a 10% discontinuation rate, 172 patients (86 patients per treatment group) were planned to be randomized in the study.  Study recruitment was discontinued at 87 patients due to challenges to enrollment and not for any safety concerns.	Clarification to the sample size as study enrollment was discontinued due to challenges to recruitment prior to reaching the target sample size.
Section 9.2.4 Per-Protocol Analysis Set		I
The per-protocol (PP) analysis set is a subset of the ITT analysis set including only patients without any major protocol deviations or unexpected drug concentration findings. Major protocol deviations will be determined before unblinding and database lock.	The per-protocol (PP) analysis set is a subset of the ITT analysis set including only patients without any major protocol deviations. Major protocol deviations will be determined before unblinding and database lock.	The definition of the per-protocol analysis set was modified as this is a subset of patients who completed the study as intended, only with a lack of major protocol deviations.
In the PP analysis set, treatment will be assigned based on the treatment patients actually received, regardless of the treatment to which they were randomized.		

Original text with changes shown	New wording	Reason/Justification for change

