Patients randomized to fremanezumab will receive 675 mg of fremanezumab administered as 3 sc injections (225 mg/1.5 mL each) at visit 2 (week 0), visit 3 (week 4), and visit 4 (week 8). randomization), visit 3 (week 4), and visit 4 (week 8). Patients will then enter the open-label period of the study, where they will receive 675 mg of fremanezumab administered as 3 sc injections (225 mg/1.5 mL each) at visit 5 (week 12), visit 6 (week 16), and visit 7 (week 20).	Patients randomized to fremanezumab will receive 675 mg of fremanezumab administered as 3 sc injections (225 mg/1.5 mL each) at visit 2 (randomization), visit 3 (week 4), and visit 4 (week 8). Patients will then enter the open-label period of the study, where they will receive 675 mg of fremanezumab administered as 3 sc injections (225 mg/1.5 mL each) at visit 5 (week 12), visit 6 (week 16), and visit 7 (week 20).	These changes were made to include the injection schedules and doses for both the blinded period and the open-label period.
Section 5.4 Treatment After the End of the Study		Land
A telephone visit will take place approximately 24 weeks following administration of the first dose of IMP to assess efficacy.	Deleted text	The follow-up telephone visit was removed from the study. There will be no follow-up visit in the adjusted study.
Section 5.6 Prior and Concomitant Medication or Therapy		
For daily-prescribed medications and preventative treatments , patients must be on a stable dose and regimen for at least 2 weeks prior to screening and maintained throughout the study until the completion of visit 58 .	For daily-prescribed medications and preventative treatments, patients must be on a stable dose and regimen for at least 2 weeks prior to screening and maintained throughout the study until the completion of visit 8.	This change was made to include the allowance of preventative treatments concomitantly with the dosing regimen.

Original text with changes shown	New wording	Reason/Justification for change
Section 5.8 Randomization and Blinding (Other sections affections)	cted by this change: Section 4.1, 4.5, and 6.1)	

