### **5.3. Demographics and Baseline Characteristics**

The demographic data will be collected at the screening visit after the patient signs the informed consent form. Patient demographic data including age, age group (<65 or ≥65 years old), gender, race, race group (white or other), ethnicity, baseline weight (kg), baseline height (cm), and baseline body mass index (kg/m^2) will be summarized using descriptive statistics for all analysis sets.

Baseline characteristics including time since the head trauma, duration of PTH history (less than 12 month since the brain injury versus greater or equal to 12 month since the brain injury), diagnosis of PTH, preventive medication use (yes or no) at screening or baseline, use of any acute headache medication (opioid, barbiturate, triptan, and NSAIDS) during the baseline period (yes or no), use of prescription abortive headache medication (opioid, barbiturate, and triptan) during the baseline period (yes or no), and monthly average number of headache days of at least moderate severity during the baseline period will be summarized for the ITT analysis set using descriptive statistics. No inferential analyses will be performed.

The time (in year) since the head trauma will be calculated as (the date of informed consent – the date of head trauma + 1)/365.25. Rules for handling partial head trauma date are in Section 4.3.

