### 6.2.2. Primary Efficacy Analysis

The hypothesis testing for the primary analysis is:

$$H_o : \delta_1 = \delta_2 \quad \text{vs} \quad H_a : \delta_1 \neq \delta_2$$

where  $\delta_1$  and  $\delta_2$  are the estimates of mean change from baseline in the monthly average number of headache days of at least moderate severity for the fremanezumab treatment group and the placebo group, respectively.

The primary endpoint will be analyzed using an ANCOVA method. The model will include treatment as fixed effect and the baseline monthly average number of headache days of at least moderate severity and the posttraumatic headache onset (<12 months and  $\geq$ 12 months) as covariates. The least square (LS) mean and SE for each treatment group, LS means and corresponding 95% confidence intervals for the treatment differences (fremanezumab - placebo), and associated p-values will be presented.

The analysis will be performed on the FAS and PP analysis sets.

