#### Example SAS code for ANCOVA

```
PROC MIXED DATA=<name>;
  CLASS TRTP ONSET;
  MODEL CHG= BASE ONSET TRTP /S;
  LSMEANS TRTP /DIFF=CONTROL ("Placebo") CL ALPHA=0.05;
  ODS OUTPUT LSMEANS= <name> DIFFS= <name> ;
RUN;
```

Where TRTP denotes the planned treatment group; CHG denotes the change from baseline in the monthly average number of headache days of at least moderate severity; BASE denotes the baseline monthly average number of headache days of at least moderate severity; ONSET denotes the posttraumatic headache onset (<12 months and  $\geq$ 12 months). In bold are the SAS key words.

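### Preventive headache medication is allowed and recorded at baseline but absent from the primary model; adding it would gain a little precision and guard against a chance imbalance among 87 patients

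*Protocol*

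**What the plan says.** Preventives are allowed in the current protocol text. Inclusion criterion h (Section 4.1) admits patients who are off preventives or on a stable regimen. Section 5.6 and Appendix F both require that regimen to be held until visit 8. The Amendment 01 log (Section 16.6) gives the reason for its edit to Section 5.6: "This change was made to include the allowance of preventative treatments concomitantly with the dosing regimen".

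SAP 5.3 lists "preventive medication use (yes or no) at screening or baseline" among the baseline characteristics and confines that list to descriptive summary.

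Randomisation is 1:1, stratified only by duration of posttraumatic headache (PTH), below or from 12 months (Protocol 5.8, SAP 2.1). For the primary ANCOVA, SAP 6.2.2 says "The model will include treatment as fixed effect and the baseline monthly average number of headache days of at least moderate severity", plus PTH onset. The example code is "MODEL CHG= BASE ONSET TRTP /S". The MMRM in SAP 6.2.3 has the same two baseline terms. No visible text stratifies by preventive use, adjusts for it or analyses the effect by it. Most of SAP 6.4 is redacted, but its visible contents list shows no such analysis.

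**The concern.** The sample mixes patients on and off a background preventive, and the plan collects the variable that separates them. A patient who still has 8 or more qualifying headache days while on a preventive may improve by a different amount over 12 weeks than an untreated patient with the same baseline count. If so, preventive use predicts the outcome. Leaving it out of the model keeps its variance in the residual, and any difference between the arms in the share of users moves the observed treatment difference.

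This matters more because recruitment stopped at 87 of the 172 planned, which makes a sizeable imbalance more probable. At stake is the precision and credibility of a proof-of-concept estimate. If the baseline table shows a gap, no pre-specified adjusted analysis will exist, and one added afterwards would be post hoc.

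**Working it through.** **1. The plan's own figure.** The Section 9.1 text, as reproduced in Protocol 16.1, claims "80% power to detect a treatment difference of 2.0 days in the monthly average". Its other inputs are an SD of 4.4 days in both arms and a two-sided alpha of 0.05. It gives "A sample size of 154 patients (77 evaluable patients per treatment group" evaluable, then "Assuming a 10% discontinuation rate, 172 patients (86 patients per treatment group" randomised.
- The normal approximation gives n = 2 × (1.960 + 0.842)² × 4.4² / 2.0² = 76 per arm. The noncentral t gives power 0.800 at 77 per arm, so the stated 77 reproduces.
- 154 / 0.90 = 171.1, which rounds up to 172. This also reproduces.

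**2. At 87 patients**, taken as 43 and 44 with no dropout:
- Standard error of the difference = 4.4 × √(1/43 + 1/44) = 0.94 day.
- Power for 2.0 days = 55% (noncentral t; 56% by the normal approximation).

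**3. Assumptions.** The documents give neither the share of users (p) nor the difference in mean change between users and non-users at equal baseline (g). I take p = 0.2 to 0.5 and g = 1 to 3 days. The total SD of 4.4 includes the part due to preventive use.

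**4. Chance imbalance.** SD of the gap between arms = √[p(1−p)(1/43 + 1/44)].

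| p | SD of gap | P(gap > 10 points) | P(gap > 15 points) | Shift at 1 SD, g = 1 / 2 / 3 (days) |
|---|---|---|---|---|
| 0.2 | 0.086 | 24% | 8% | 0.09 / 0.17 / 0.26 |
| 0.3 | 0.098 | 31% | 13% | 0.10 / 0.20 / 0.29 |
| 0.5 | 0.107 | 35% | 16% | 0.11 / 0.21 / 0.32 |

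At the planned 172, the chance of a gap above 10 points would be 10-19%. At the 95% extreme of imbalance with 87 patients (17 to 21 points), the shift is 0.17-0.21 day for g = 1 and 0.50-0.63 day for g = 3.

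**5. Gain from adjustment.** Share of residual variance = p(1−p)g² / 4.4².
- Smallest: 0.16 × 1 / 19.36 = 0.8%. Largest: 0.25 × 9 / 19.36 = 11.6%.
- The adjusted SD runs from 4.38 down to 4.14, the standard error from 0.94 down to 0.89 day, and power is 56% to 61% (noncentral t).
- If g = 0, one extra degree of freedom takes power from 55.38% to 55.37%.

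**6. What passes through the planned model.** I simulated 87-patient trials with 30% users, 8,000 per scenario, without the stratification, and regressed the treatment estimate on the gap in users.
- Users 3 days higher at baseline, g = 0: slope about −0.1, so essentially nothing passes through.
- g = 2 and g = 3: slopes about 2 and 3 under the planned model, and close to 0 (at most 0.2) once preventive use is in it.
- With no treatment effect, type I error was 4.7-5.7% (planned) and 4.8-5.2% (adjusted). A repeat with 200,000 trials per scenario gave 5.0-5.1% for both models. The planned estimate was unbiased on average.

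**The case against.** The strongest reply is that nothing is wrong with the planned analysis. The endpoint is change from baseline, and the model adjusts for baseline headache days that are recorded while the patient is already on the stable preventive. Holding the regimen to visit 8 keeps background treatment constant across the comparison. No passage says that stable use predicts change at equal baseline. Use is tabulated by arm, so a gap would be seen. The assumed effects have no source, 3 days exceeds the 2.0-day target, and the fall from 80% to about 55% power comes from stopping at 87, which a covariate cannot repair.

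Most of this stands, and it rules out three inferences that a reader might draw:
- That an imbalance goes straight into the result. Only the part not explained by baseline headache days does.
- That the standard error ignores the imbalance. The omitted variance stays in the residual, so the standard error already reflects it.
- That an imbalance is likely. A gap above 10 points has a 24-35% chance.

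Nor does the stability rule show that the protocol regards preventive use as prognostic; it controls changes in treatment during the trial.

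The reply also notes that the edit is wider than one model line and that the variable needs a definition. Both are correct and are covered in the fix. Neither is a reason to leave out a baseline variable that is already collected and costs almost nothing to include.

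**Conclusion.** The point holds as a small, nearly free improvement. The primary analysis is valid as planned. It gives up some precision, and protection in the one realised sample, if preventive use predicts change at equal baseline. Under the assumed ranges a 1-SD imbalance shifts the estimate by at most about a third of its standard error (0.32 / 0.94), and the power gain is about 1 to 6 points. If g is near zero, nothing is gained and almost nothing is lost. The documents do not support calling this a bias or an inflated error rate. The value lies mainly in having the adjusted analysis fixed before anyone sees the baseline table by arm.

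**What to change.** Before unblinding:
- Add baseline preventive use (yes/no, SAP 5.3) as a fixed effect in the ANCOVA of SAP 6.2.2, with PREV added to the CLASS statement and the model written as MODEL CHG = BASE ONSET PREV TRTP. Add it to the MMRM of SAP 6.2.3, which 6.3.3 follows. State whether the HIT-6 model in 6.3.4, defined by analogy with 6.2.2, takes it too.
- Define the variable in one line. SAP 5.5 separates listed preventives taken for PTH from those taken for other reasons; say whether the latter count.
- Carry the change into SAP 1.6 (estimand component 4), SAP 17 (which now lists no changes) and the primary analysis text in the protocol synopsis and Section 9.5.5.1.
- At minimum, keep the planned ANCOVA as primary and pre-specify the model with PREV as a sensitivity analysis.

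Reconcile the stability periods as well, since they bear on who is a stable user: 2 months before the baseline period (inclusion h), 2 weeks before screening (Section 5.6), and started at least 2 months before screening (Appendix F).

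Cost: one degree of freedom, a few lines of text and no new data.
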